3.1. Table 2. Objectives and endpoints

Objectives	Endpoints
Primary	
To assess the effects of phenserine compared to donepezil on exosome biomarkers of cell death in people with early or mild AD.	Changes in endosomal biomarkers of pre-programmed cell death, synaptic integrity and function, neuroinflammation, and AD-related protein trafficking in participants treated with phenserine versus those treated with donepezil. Although patients and site staff will be unblinded to the treatment modality administered, they will be blinded to the results of the biomarker evaluations until the study is completed.
Secondary	
To evaluate the safety and tolerability profile of phenserine at ascending doses up to 10 mg tds as compared to donepezil at doses up to 10 mg od in participants with early or mild AD.	Safety and tolerability of phenserine compared to donepezil in participants with early or mild AD based on the frequencies of reported or observed adverse events (AEs) and serious adverse events (SAE), vital signs, clinical laboratory evaluations, ECGs, modified CSSRS scores.
Other secondary	
To evaluate steady state blood levels of phenserine and donepezil for the purpose of characterizing and comparing dose-response relationships for pharmacodynamic outcomes and key safety assessments.	Pharmacokinetic parameters will be assessed at steady state for determination of dose-response relationships for phenserine and donepezil
To evaluate the proportion of participants in the phenserine arm who achieve the target cholinesterase inhibition of approximately 45% across different dosing regimens, as well as the time required to reach the target and the duration of maintaining this inhibition.	Proportion of participants in the phenserine arm achieving the target cholinesterase inhibition of ~45%, stratified by dosing regimen and the time to reach the target inhibition and the duration of maintaining this target will be assessed and recorded
To evaluate compliance, the study will measure the extent to which participants	Compliance will be recorded, based on drug count and subject diary, including the proportion of

take the study medication according to the protocol. Compliance will be assessed using the subject diary and the registration of returned capsules.	participants complying with the treatment schedule. Compliance is defined as drug intake within 80-120% of the scheduled dosing.
Exploratory	
To evaluate disease modification by assessing changes in specific biomarkers of Alzheimer's Disease (AD) in cerebrospinal fluid (CSF): A β 1-40, A β 1-42, Tau, and p-tau, and in blood plasma: p-tau217 and Nfl.	Assess changes in Alzheimer's Disease (AD) biomarkers in cerebrospinal fluid (CSF): A β 1-40, A β 1-42, Tau, and p-tau, and in blood plasma: p-tau217 and Nfl.
To assess phenserine's potential short-term effects on specific cognitive tasks using the FLAME Memory Composite and other cognitive sub-tests	Neuropsychology assessments will be conducted using the FLAME computer-based domain composites for memory, executive function, attention and sustained attention to evaluate changes over the 8-week treatment period in the phenserine treated participants compared to those who received donepezil.
To assess effect on global cognition	The Montreal Cognitive Assessment (MoCA) will be administered at baseline and at the end of the study to evaluate changes in overall cognitive function across multiple domains, including visuospatial abilities, language, attention, memory, and executive function.

3.2. Outcome Measures

3.2.1. Primary Outcome Measure

The primary outcome measure will assess changes in four panels of exosome biomarkers, including markers of pre-programmed cell death, synaptic integrity and function, neuroinflammation, and AD-related protein trafficking in participants treated with phenserine versus those treated with donepezil. Panel details are presented in separate standardized operationalized procedures (SOPs).

Although participants and site staff will be unblinded to the treatment modality administered, they will be blinded to the results of the exosome and blood/CSF biomarker evaluations until the study is completed.

The pre-programmed cell death panel (PNCDD) will investigate key factors such as BAX, Bcl-2, which will provide insights into preprogrammed cell death processes (4,17) and any changes in the profile observed following treatment with phenserine or donepezil. The second panel focuses on synaptic markers, including synaptotagmin, offering a nuanced understanding of synaptic integrity and function. The third panel is centered on evaluating inflammatory biomarkers, including TNF- α , IL-1 β , IL-6, and IL10, and the fourth panel will evaluate AD-specific markers, including A β 1-42, and will elucidate key molecular signatures associated with AD pathology. This comprehensive evaluation of mechanistic biomarkers through exosome technologies aims to deliver a detailed understanding of the impact of phenserine versus donepezil on various facets of AD neuropathology, contributing to the trial's primary objective.

3.2.2. Secondary Outcome Measures

The key secondary outcome in this study is the safety and tolerability profile of phenserine at ascending doses up to 10 mg tds as compared to donepezil at doses up to 10 mg od in participants with early or mild AD. Safety data will be collected through measurements of vital signs, physical and neurological examinations, clinical safety laboratory tests (including hematologic analyses for urea and electrolytes, creatinine, liver function tests, and full blood count as well as urinalysis), ECG parameters, and suicidality using a modified shortened version of the Columbia Suicide Severity Rating Scale (C-SSRS) (23).

Adverse events will be recorded following completion of informed consent. Qualified personnel will code adverse events using the lowest level term according to MedDRA (version 19.0) and by duration, severity grade, relationship to the study drug, the action(s) taken, and outcome.

Information about all serious adverse events will be collected. A serious adverse event (SAE) is an undesirable sign, symptom, or medical condition that is fatal or life-threatening, requires hospitalisation, results in persistent or significant disability/incapacity, constitutes a congenital anomaly or birth defect, or is medically significant. A Suspected Unexpected Serious Adverse Reaction (SUSAR) is any adverse reaction that is classed as serious and suspected to be caused by the investigational medicine that is not consistent with previously established safety information (i.e., it is suspected and unexpected). To ensure participants' safety, each SAE will be reported to the data monitoring committee within 24 hours (h) of the trial staff learning of its occurrence and SUSARs will be reported in accordance with regulatory requirements.

Tolerability will primarily be assessed based on reported AChEI-related adverse events (24) during the dose escalation phase of the study. Based on these measurements, doses will be escalated for the phenserine arm to achieve a maximum tolerated dose.

Assessments will be completed at site before the participant is cleared for the next dose level. This decision will be made based on tolerability and safety blood testing and ECG. If laboratory data coming after the visit indicate the need to revise this decision, then the participant will be contacted. The responsible study physician will be responsible for this decision, if needed, after consultation with the local PI, the medical monitor, or the study PI.

PK parameters will also be assessed as a secondary outcome measure. Blood samples for PK analyses will be collected at steady state for determination of dose-response relationships for phenserine and donepezil.

Compliance will be recorded as the proportion who comply with the intake of IMP, defined as between 80-120% of the scheduled dosing. Compliance will be measured by counting the returned capsules and a subject diary.

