A second smaller RCT randomized 20 AD- patients equally to phenserine or placebo for 3 months. The placebo group then received donepezil after 12 weeks in an open design. Participants receiving phenserine had significantly greater improvements in cognition and improvements in cerebral glucose metabolism compared to the group treated with placebo, and the cognitive benefits were maintained after 6 months compared to the group receiving donepezil for the second 3 months of the trial (8).

Although these data are encouraging, the compound has not been assessed in people with early or mild AD, and the potential for disease modification has not previously been evaluated in human clinical trials.

From a safety perspective, in the larger trial with 72 participants, 77% of patients completed the study protocol. The overall discontinuation rate for the 15 mg twice daily group (23.6%) was only slightly higher than for the placebo group (17.1%). Withdrawals due to adverse events were slightly lower in the 15 mg twice daily group (5.9%) than in the placebo group (6.1%). Nausea (9% 10mg bd, 19% 15mg bd) and vomiting (5% at 10mg bd and 11% at 15mg bd) were the most common AEs in the active drug treated groups but did not contribute to dropouts and are comparable to rates for licensed cholinesterase inhibitors (3).

In a further single escalating dose safety study, 32 healthy elderly volunteers received single oral doses of phenserine tartrate up to 20 mg(5). Physical and vital signs were monitored over the ensuing 24 hours. Analyses were performed on plasma samples to determine PK, and PD effects were assessed as a function of AChE levels. No serious adverse events (SAEs) occurred; the most common AEs were headache and vomiting. Evaluation of PK/PD relationships suggested a linear correlation between plasma phenserine concentration and AChE inhibition. Other phase 1 studies indicated that the peak AChE effect occurs 30 minutes after dosing, with a maximum AChE inhibition of about 30% with a 10 mg dose. Food delayed t_{max} from 1.4 hr. to 2.7 hr compared to fasting.

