2.3.4. Overall Benefit Risk Conclusion

Overall, there is strong pre-clinical evidence of phenserine's biological effects that are relevant to the treatment of AD and other neurodegenerative conditions, with a novel effect on apoptosis in addition to cholinesterase inhibition. Previous clinical trials with phenserine suggest a good clinical safety profile and offer some encouraging indications of potential benefit. The protocol has been designed based on the learnings of the failed Axonyx program and will ensure that the patient population is appropriate and that the study assessments more fully characterize phenserine's potential therapeutic utility across more robust measures of pharmacodynamic effects and any correlated improvements in cognitive function.

3. Objectives, and Endpoints

The study will be conducted as a 2 arm, parallel group, randomized RCT of phenserine compared to donepezil in people with early or mild AD. A total of 16 participants will be recruited from sites across Norway and be supported by the PROTECT platform. Eligible participants will be randomized 6:2 to phenserine or donepezil in an unblinded manner.

The end of the research active period for this study is set to January 1, 2028. All analyses within the scope of this study will be completed by this date.

The pharmacodynamic (PD), pharmacokinetic (PK), and safety data from this study are intended to inform dose selection and study design for a subsequent Phase 2 study of phenserine over a longer treatment duration in people with early to mild Alzheimer's disease (AD). The objectives of the study are as follows:

Primary Objective:

To assess the effects of phenserine compared to donepezil on exosome biomarkers of cell death in people with early or mild AD.

Key Secondary Objective:

To evaluate the safety and tolerability profile, of phenserine at ascending doses up to 10 mg tds as compared to donepezil at doses up to 10 mg od in participants with early or mild AD.

Other Secondary Objectives:

To evaluate steady state blood levels of phenserine for the purpose of characterizing and comparing dose-response relationships for pharmacodynamic outcomes and key safety assessments.

To evaluate the proportion of participants in the phenserine arm who achieve the target AChE inhibition of approximately 45%, stratified by dose regimen and the time required to reach the target AChE inhibition of ~45% and the duration participants maintain this inhibition during the treatment period.

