6.1.2. Table 4. Study Arm(s)

Arm Title	Start dose	Maintenance dose	Donepezil	Maintenance of Donepezil
Arm Type	intervention	Intervention	Comparator	Comparator
Arm Description	Participants will receive 5mg mg bd on Week 1-2	Participants will receive 10 mg bd from Week 3-4 10 mg TDS from Week 5-8	Participants will receive 5mg od from week 1-4	Participants will 10mg od from week 5

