6.6. Dose Modification

As shown in the Study Schema (Figure 1), participants randomized to the phenserine arm will initiate dosing at 5 mg bd and maintain this dose for the first two weeks of study treatment. At the Week 3 visit, participants may be escalated to 10 mg bd, then 10mg tds (Figure 1), based on tolerability, including adverse events, clinical assessment, ECG and safety laboratory measurements. Participants who are unable to tolerate a higher dose will have their dose reduced to the next previous dose level and maintained at that dose through the remainder of the study. This clinical decision will be made by the study physician and the study team at each centre at the visit, or when any safety laboratory results are received during the days after the visit. If needed, the medical monitor and the PI will be contacted. All participants are expected to be at their individualized maintenance dose for 4 weeks (beginning of Week 5 through the end of Week 8).

Participants randomized to the donepezil arm, will initiate dosing at 5 mg od and will be evaluated at the Week 4 visit for dose escalation to 10 mg once daily. For participants in the phenserine arm, dosing will follow a stepwise escalation to ensure safety and efficacy:

- **Weeks 1-2:** Participants will begin with 5 mg twice daily (bd).
- **Weeks 3-4:** Participants will escalate to 10 mg twice daily (bd) if the initial dose is well tolerated.
- **Weeks 5-8:** Participants will further escalate to 10 mg three times daily (tds) based on continued tolerability.

Before any dose escalation, the dosage will be reassessed based on tolerability. If necessary, participants may be required to return to the center for a dose reduction. Throughout the study, dose adjustments will be made according to tolerability. Should any dose escalation lead to adverse effects that compromise the participant's well-being or safety, the dose will be reduced to the previously well-tolerated level. Participants will then continue at this adjusted dose for the remainder of the study period. These procedures are outlined in more detail in the dedicated SOP.

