2.3 Exploratory Objectives

- Changes in CSF and plasma AD biomarkers
- Short-term cognitive effects using FLAME and MoCA

Endpoints are defined exactly as per Protocol Section 3 and Table 2

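### Protocol 3.2.2 ties tolerability to an undefined dose escalation phase, which conflicts with the endpoint and SAP timeframe, and SAP 8.1 drops the promised summary by dose level

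*Protocol*

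**What the plan says.** The key secondary objective in Protocol Section 3 is to compare safety and tolerability "of phenserine at ascending doses up to 10 mg tds as compared to donepezil at doses up to 10 mg od".

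Under Secondary Outcome Measures, Protocol 3.2.2 gives the basis for judging tolerability: "Tolerability will primarily be assessed based on reported AChEI-related adverse events (24) during the dose escalation phase of the study". The next sentence says that, on these measurements, "doses will be escalated for the phenserine arm to achieve a maximum tolerated dose".

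On timing, Table 4 puts the highest phenserine level under the maintenance dose: "10 mg TDS from Week 5-8". Protocol 6.1 and Table 4 start donepezil 10 mg od in Week 5. Section 6.6 adds: "All participants are expected to be at their individualized maintenance dose for 4 weeks (beginning of Week 5 through the end of Week 8". The Schedule of Activities lists a dose review, for a step up or down, at Weeks 2, 4 and 6.

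Other places set no such window. The endpoint in Section 3 and Table 2 is the frequency of AEs and SAEs, with vital signs, laboratory tests, ECGs and the C-SSRS. Protocol 9.17.1 collects AEs from first treatment to the last follow-up visit. SAP 4.5 gives safety and tolerability a timeframe covering the entire study. SAP 2.3 says: "Endpoints are defined exactly as per Protocol Section 3 and Table 2".

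On presentation, Protocol 10.3 promises safety summaries for each arm and each dose level. SAP 8.1 lists summaries by arm only, including gastrointestinal AEs, dose reductions and discontinuations.

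**The concern.** The objective reaches up to the top dose of each drug, but the sentence naming the primary basis for tolerability points to a period that, read naturally, ends before those doses begin. An analyst told to follow Section 3 exactly finds both an endpoint without a window and a sentence with one there, and then a whole-study timeframe in SAP 4.5. All three cannot be followed.

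The SAP does not resolve this. Even with the whole-study timeframe, its by-arm table gives the same count whether a cholinergic event began on the starting dose or on 10 mg tds. The trial is meant to inform the Phase 2 dose range, so tolerability by dose level is what its readers will need.

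**Working it through.** **1. The plan's own figure.** Section 6.6 gives 4 weeks at the maintenance dose, from the start of Week 5 to the end of Week 8. That is 4 × 7 = 28 of 8 × 7 = 56 days, or 50%. It agrees with Tables 3 and 4.

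**2. Planned exposure (Protocol 6.1, Tables 3 and 4).**
- Phenserine: 14 days × 10 mg + 14 days × 20 mg + 28 days × 30 mg = 140 + 280 + 840 = 1260 mg. The top-dose share is 840/1260 = 66.7%.
- Donepezil: 28 days × 5 mg + 28 days × 10 mg = 140 + 280 = 420 mg. The top-dose share is 280/420 = 66.7%.

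**3. Top-dose days inside the tolerability window.** The top dose starts after Day 28, so the days inside are max(0, end of window − 28).

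| Reading of the window | Ends on | Top-dose days inside |
|---|---|---|
| Escalation ends at the Week 4 visit | Day 28 | 0 of 28 |
| Escalation runs to the Week 6 dose review | Day 42 | 14 of 28 |
| Whole treatment period | Day 56 | 28 of 28 |

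These are nominal days; visits may shift by ±3 days.

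**4. Which reading fits the text.** The last planned step up is at the Week 4 visit (Protocol 6.3), and Section 6.6 calls Weeks 5 to 8 maintenance. SAP 3.4.2 lists stopping treatment before the escalation phase is complete as a deviation, so it treats the phase as something that finishes. This favours Day 28. The Week 6 review, which allows a step up or down, keeps Day 42 possible. No text settles it.

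**5. Summary level.** Protocol 10.3: arm and dose level. SAP 8.1: arm only. SAP Section 11 does not list this as a change from the protocol.

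**6. Scale, for illustration only.** Protocol 2.3.1 reports "Nausea (9% 10mg bd, 19% 15mg bd) and vomiting (5% at 10mg bd and 11% at 15mg bd" from an earlier trial. Suppose all 12 phenserine participants reach 10 mg tds and the nausea rate there is p. Expected cases are 12p, and the chance of at least one is 1 − (1 − p)^12.
- p = 19%: 12 × 0.19 = 2.3 cases; 1 − 0.81^12 = 92%.
- p = 5%: 0.6 cases; 46%.
- p = 30%: 3.6 cases; 99%.

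The 19% belongs to 15 mg bd over 12 weeks, and the protocol expects three smaller doses to lower the rate. The range is therefore a better guide than the single figure.

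**The case against.** The strongest reply is that the sentence in 3.2.2 describes the input to titration, not the reporting window. The sentence after it speaks of escalating to a maximum tolerated dose, and the text that follows covers clearance for the next level. For that purpose, events during escalation are the relevant ones, and the word primarily does not mean only. The labelled endpoint, which the SAP imports, has no window. The objective names a range of ascending doses, not the top one alone.

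Much of this stands. A reader might infer that someone who first becomes intolerant in Weeks 5 to 8 goes uncounted, or that the tolerability conclusion does not depend on top-dose events. The documents do not support that. AEs are collected to the last follow-up visit, SAP 4.5 covers the whole study, and SAP 8.1 counts dose reductions and discontinuations without a time limit. The only numeric tolerability rule, in Protocol 2.3.1, counts dose-limiting effects at 10 mg tds itself. Apart from that rule there is no tolerability threshold; the analysis is descriptive.

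What the reply does not remove is the wording. The sentence sits under Secondary Outcome Measures and states how a key secondary outcome is primarily assessed. If it is meant only for titration, it should say so. The down-titration and capping rules govern conduct, not how the outcome is reported. Nothing in the reply restores the dose-level summary missing from SAP 8.1.

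**Conclusion.** The point holds as an inconsistency to reconcile, together with a lost level of detail in the SAP. The tolerability window in 3.2.2 is undefined, and its most natural reading contains 0 of 28 top-dose days in either arm, leaving out half of treatment time and two-thirds of scheduled drug. If the phase runs to Week 6, 14 of 28 top-dose days are still outside. Either reading conflicts with the endpoint definition, SAP 4.5 and an objective that extends to the top doses.

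These figures assume the nominal schedule and that participants escalate as planned. The consequence is limited: top-dose events stay in the safety data, but under SAP 8.1 they are pooled within arm across dose levels. The nausea range of 0.6 to 3.6 cases in 12 rests on assumed rates of 5% to 30% and only indicates how many events the split might concern.

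**What to change.** - **Protocol 3.2.2:** state that tolerability as an outcome covers the whole treatment period. Keep the use of AChEI-related AEs for titration decisions in a separate sentence. If the term dose escalation phase stays there or in SAP 3.4.2, define its start and end.
- **SAP 8.1:** summarise AChEI-related AEs, dose reductions and discontinuations by arm and by dose level at onset, with the number of participants and the days exposed at each level. This restores what Protocol 10.3 promises. It is more informative than splitting Weeks 1–4 from Weeks 5–8, which would pool 5 mg bd with 10 mg bd and mix 10 mg tds with participants held at or returned to lower levels.

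The cost is one protocol sentence and one extra split in a planned table. AEs are already recorded at the Week 6 and Week 8 visits, so no new data are needed. The downside is that reported tolerability at the top dose may look less favourable. No dose, titration rule or stopping rule changes.

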3.2.3. Exploratory Outcome Measures

Neuropsychology assessments will be conducted using the FLAME computer-based domain composites for memory, executive function, attention and sustained attention to evaluate changes over the 8-week treatment period in the phenserine-treated participants compared to those who received donepezil. The results of these assessments will be compared to changes observed on exosome biomarkers to identify similar trends across the treatment arms and in individual participants.

In addition, the Montreal Cognitive Assessment (MoCA) (24) will be used at baseline and end-of-treatment to assess for any changes in cognition over the course of the treatment period.

CSF or blood AD or Tau markers or amyloid PET will be analyzed for typical AD features as an inclusion criterion (see Section 5). Blood will also be collected at the Week 8 visit to evaluate any changes in blood-based biomarkers across the two groups. Among consenting participants, CSF will also be collected and stored for evaluation of CSF-specific biomarker changes. All procedures will be performed according to highly standardized procedures in accordance with the defined biobanking pre-analytical standard operating procedures (SOPs) of the BIOMARKAPD project (25).

4. Study Design

